Photography of both hands back and front including the wrist ¹⁶		X					X	X		X						8.1.4
End of treatment/trial																_
End-of-treatment form										X						8.10.1
End-of-trial form ¹⁷										(X)	X	X		(X)	(X)	8.10.2

- 1. End-of-treatment assessments will be conducted at Week 24. Participants who permanently discontinue the IMP or who withdraw from the trial prior to Week 24 will be asked to return to the trial site for an ET visit as soon as possible after the last dose for completion of all trial procedures scheduled for the visit at Week 24.
- 2. All participants will be asked to return to the trial site approximately 2 weeks after the last dose of IMP for assessment of safety at a follow-up visit.
- 3. For WOCBP treated with alitretinoin, only.
- 4. Participants who permanently discontinue the IMP prior to Week 12 will be asked to return to the trial site at Week 12 for a primary endpoint visit and at Week 24 for a nominal Week 24 visit. Participants who permanently discontinue the IMP between Week 12 and Week 24 will be asked to return to the trial site for a nominal Week 24 visit.
- 5. Unscheduled visits occur if participants need to make a visit in between the scheduled visit dates, e.g. for reading of a patch test, due to an AE, or due to a significant change in their disease state. Assessments to be performed at unscheduled visits will be at the discretion of the unblinded investigator.
- 6. For participants treated with medications requiring a 28-day washout period prior to baseline (see Table 6-2), the duration of the screening period may be extended up to 31 days to ensure appropriate washout. For WOCBP the duration of the screening period may be extended up to 42 days to ensure compliance with contraceptive and pregnancy prevention programme requirements.
- 7. For participants who have not had a patch test within 3 years prior to screening, the patch test should be completed so results are available prior to baseline assessments (Day 1).

- 8. Completion of the HESD component of the eDiary will be initiated at least 1 week prior to baseline (Day 1), but preferably from the date the participants receive the eDiary. Compliance with the eDiary completion will be reviewed by the trial site staff throughout the trial. Participants who permanently discontinue the IMP but remain in the trial will continue completing the eDiary until the nominal Week 24 visit.

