Safety assessments, adverse events, and treatment decisions will be made by the unblinded investigator to allow for:

- Dose reductions for participants treated with alitretinoin (Section 6.5).
- Permanent IMP discontinuation (Section 7.1).
- Decisions to continue, stop or restart the IMP from Week 16 for delgocitinib or Week 12 for alitretinoin (Section 6.5.1).

Participants will stop the IMP if they achieve an IGA-CHE score of 0 (clear) or 1 (almost clear) after 16 weeks of delgocitinib treatment or 12 weeks of alitretinoin treatment. Participants who discontinued delgocitinib treatment due to IGA-CHE score of 0 or 1 must restart treatment if they relapse to an IGA-CHE score of ≥2. These participants will continue attending the treatment period visits as planned until Week 24.

Participants who permanently discontinue the IMP will attend an ET visit, they will stop attending the treatment period visits and will only be asked to return to the trial site at Week 12 for a primary endpoint visit and at Week 24 for a nominal Week 24 visit.

Follow-up period: Approximately 2 weeks after the last dose of IMP, participants will attend a follow-up visit for safety assessments. Women of childbearing potential treated with alitretinoin will attend an additional follow-up visit for a pregnancy test, 5 weeks after the last dose of alitretinoin

Refer to Section 10.5 for coronavirus disease 2019 (COVID-19) pandemic contingency plan.

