Delgocitinib application on initially affected area(s) and new lesions will continue until Week 16 regardless of clearance status. Participants with an IGA-CHE score ≥2 may continue with treatment up until Week 24 if, in the opinion of the unblinded investigator, they may benefit from continued treatment. After Week 16, it is recommended to discontinue delgocitinib if IGA-CHE is 0 (clear) or 1 (almost clear). Participants who discontinued delgocitinib treatment due to IGA-CHE score of 0 or 1 must restart treatment if they relapse to an IGA-CHE score of ≥2. These participants will remain on continuous treatment until Week 24. Treatment with delgocitinib should be discontinued if participants still have an IGA-CHE score of 4 (severe) after the initial 16 weeks of treatment.

Prior to each trial visit, application of delgocitinib cream will occur at the participant's home at least 2 hours prior to the trial visit.

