8.2.7.1 Participant's Assessment of Local Tolerability

The participant will complete a weekly assessment of stinging/burning in connection with the delgocitinib cream applications in the eDiary. The participant will be asked to retrospectively assess the worst stinging/burning in connection with the delgocitinib cream application during the last week. In addition, the participant will be asked by the unblinded investigator at the End of Treatment/Early Termination visit to assess the local tolerability during the last week (see Section 1.3). The assessment will be done using the 4-point scale shown in Table 8-8.

Table 8-8 Participant's Assessment of Local Tolerability after Delgocitinib Cream Application

Grade (severity)	Stinging/burning				
0 (none)	No stinging or burning.				
1 (mild)	Slight warm, tingling sensation, not really bothersome.				
2 (moderate)	Definitive warm, tingling sensation, that is somewhat bothersome.				
3 (severe)	Hot, tingling/stinging sensation that has caused definite discomfort.				

The participant's assessment of local tolerability may be reported as an AE at the discretion of the investigator, even if the investigator does not suspect a local skin reaction related to the application of delgocitinib cream (reporting of e.g. pain or stinging/burning by the participant).

For the participant's assessment of local tolerability at the EOT/ET visit, the highest (worst) skin reaction score across treatment area(s) will be recorded in the eCRF.

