9.3.11.2 Vital Signs and Physical Examination

For vital signs (resting blood pressure, pulse, and body temperature), the absolute values at baseline and EOT/ET as well as the change from baseline to EOT/ET will be summarised for each treatment group.

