9.3.11.4 Participant's and Investigator's Assessment of Local Tolerability

Participant's and investigator's assessment of local tolerability for delgocitinib cream will be summarised by visit.

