10.9 Appendix 9: Amendments

Amendment 3 (08 Apr 2022)

Overall Rationale for the Amendment

The protocol was amended in order to implement changes from local amendments (UK and Canada).

Section # and Name	Description of Change	Brief Rationale
Section 1.3: Schedule of Activities (SoA)	Table 1-1 was updated to include the check of contraception compliance in the alitretinoin group only at all study visits (except at Day 8 and Day 15).	This was updated to address questions from Health Canada.
	A typo was corrected in footnote number 13.	
	Sub header "Participant assessment of safety" was added.	
	"Weekly" changed to "Weekly while on treatment" as many participants will not be on Delgocitinib treatment at visit 9 and 10. Footnote added to clarify this difference.	

Section # and Name	Description of Change	Brief Rationale
Section 1.3: Schedule of Activities (SoA) Section 8.2.7.1: Pregnancy Testing	Assessment added under sub-header "Participant assessments of efficacy and health-related quality of life during trial visits" to indicate an additional local tolerability assessment during visits. Addition of Participant assessment of local tolerability at End of Treatment and Early Termination visit.	Only weekly assessment of local tolerability is collected in the eDiary. Participant assessment of local tolerability is added to the End of Treatment and Early Termination visit in eCRF to ensure that participant assessment of local tolerability data is collected at these visits.
Section 1.3: Schedule of Activities (SoA) Section 2.3.1: Risk Assessment (Table 2-1) Section 5.1: Inclusion Criteria Section 10.4.2: Contraception Guidance	Additional information for footnote 6 to accommodate for the extension of the screening period for WOCBP on contraception. Text amended to clarify contraception requirements.	To ensure compliance with pregnancy prevention program for WOCBP.
Section 1.3: Schedule of Activities (SoA)	The text "alitretinoin group only" removed from mental health interview. Footnote added to Table 1-1 for clarification.	To clarify that the metal health interview is applicable for both treatment groups at Screening and Baseline.
Section 2.3.1: Risk Assessment	Text was added to report on the safety concerns for oral JAK inhibitors.	This was updated according to the latest edition of the IB.

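### Three descriptive safety summaries at Weeks 20 and 24 pool on-drug records with records from responders who have already stopped treatment

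*Combined protocol and SAP*

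**What the plan says.** **Timing of the visit.** Footnote 1 of the Schedule of Activities (SoA, Section 1.3) states: "End-of-treatment assessments will be conducted at Week 24". Participants who discontinue permanently or withdraw are handled differently: they "will be asked to return to the trial site for an ET visit as soon as possible after the last dose".

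**Planned stops.** Section 4.1 has participants stop on IGA-CHE 0 or 1 "after 16 weeks of delgocitinib treatment or 12 weeks of alitretinoin treatment" and keep to the regular visit schedule through Week 24. Section 8.10.1 counts a stop for good clearance as completed treatment, so these participants are not routed to the early-termination (ET) visit. Under Section 6.5.1, those who relapse to IGA-CHE 2 or more go back on treatment and stay on it to Week 24.

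**Local tolerability.** The delgocitinib group is "asked by the unblinded investigator at the End of Treatment/Early Termination visit to assess the local tolerability during the last week" (Section 8.2.7.1). The answer is a grade from 0 to 3 in Table 8-8, which has no category for no application. The weekly eDiary version of the item is limited to time on treatment (SoA footnote 12). The investigator's own assessment (Section 8.2.7.2) is scheduled at every treatment visit from Week 1 to Week 24. Section 9.3.11.4 says that the "assessment of local tolerability for delgocitinib cream will be summarised by visit".

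**Vital signs.** The SoA schedules them at screening, Day 1 and EOT/ET, plus optional unscheduled checks. Section 9.3.11.2 says "the absolute values at baseline and EOT/ET as well as the change from baseline to EOT/ET will be summarised for each treatment group".

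**Denominator.** Section 9.3.1 bases by-visit tables on the participants who attended the visit. It sets no condition on recent dosing.

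**The concern.** EOT is a calendar visit, not a visit tied to the last dose. A delgocitinib responder who stopped at Week 16 and stayed clear is asked at Week 24 about stinging or burning from cream in a week when none was applied. Of the grades offered, only 0 fits. The investigator's question at Weeks 20 and 24, whether a cream-related reaction is suspected, then has little to detect in that participant. Both records count in the by-visit table because the participant attended.

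The plan already recognises the problem for one data source. The amendment log explains the on-treatment limit on the weekly eDiary item: "as many participants will not be on Delgocitinib treatment at visit 9 and 10". Visit 10 is the EOT visit, yet the EOT/ET question and the by-visit summary carry no matching limit.

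The vital-sign gap is of a different kind. A responder who stops and does not restart has no scheduled on-treatment value after Day 1, and the only planned post-baseline summary uses the EOT/ET value. That summary combines participants still on drug, responders off drug for weeks, and ET participants seen soon after their last dose. Planned stops begin at Week 12 in one arm and Week 16 in the other, so the mix can differ between arms.

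Comparing safety is the trial's secondary objective. A reader of these tables should be able to tell on-drug values from off-drug values.

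**Working it through.** The plan states no figure on this point, so there is nothing to reproduce. The check has three parts.

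**1. Time off drug.** Inputs are the SoA visit days: Week 12 = Day 85, Week 16 = Day 113, Week 20 = Day 141, Week 24 = Day 169, each with a ±3-day window. Gap = assessment day minus stop-visit day; two windows together give ±6 days. The participant does not restart.

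| Stop visit | Arm | Gap at Week 20 | Gap at Week 24 |
|---|---|---|---|
| Week 12 | alitretinoin | not needed (tolerability is delgocitinib only) | 169 − 85 = 84 days (78 to 90) |
| Week 16 | delgocitinib; alitretinoin | 141 − 113 = 28 days (22 to 34) | 169 − 113 = 56 days (50 to 62) |
| Week 20 | either | 0 | 169 − 141 = 28 days (22 to 34) |

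The nominal maximum is therefore 8 weeks for delgocitinib and 12 weeks for alitretinoin. A stop at Week 20 gives 4 weeks. A participant who restarted is on drug at Week 24, with a gap of 0. The 12-week figure can apply only to vital signs, because local tolerability is not assessed in the alitretinoin arm.

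**2. Dilution of the EOT/ET stinging/burning rate.** Let p be the on-drug rate and f the share with no application in the recall week. If off-drug participants record 0, reported rate = p × (1 − f). The documents give neither p nor f. With p = 10% assumed:

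- f = 20% (0.20 × 255 = 51 participants): 10% × 0.80 = 8%
- f = 30%: 10% × 0.70 = 7%
- f = 40%: 10% × 0.60 = 6%
- f = 50% (0.50 × 255 = 127.5, about 128 participants): 10% × 0.50 = 5%

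**3. Vital signs.** Suppose, for illustration only, that both arms have the same on-drug change of 5 units and that it reverses fully off drug. Pooled mean = 5 × (1 − f). For f from 10% to 50% this runs from 4.5 down to 2.5 units. If the off-drug share were 40% in one arm and 20% in the other, the means would be 5 × 0.60 = 3.0 and 5 × 0.80 = 4.0. That is a 1.0-unit difference between arms with no difference in drug effect.

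**The case against.** A reader might infer that the delgocitinib stinging/burning rate as a whole is diluted. The documents do not support that. The main source is the weekly eDiary item, which is collected only on treatment, so its summary carries that limit with it. Only the one added EOT/ET question is exposed. Adverse events are collected throughout, and laboratory tests are repeated every 4 weeks from Week 4.

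A reader might also infer that responders in general are 8 to 12 weeks off drug at EOT. Those are per-arm maxima. Some stop later, relapsers restart, and some responders may never stop: Section 6.2.1.1 says "After Week 16, it is recommended to discontinue delgocitinib if IGA-CHE is 0 (clear) or 1 (almost clear"), which is a recommendation.

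For the investigator's assessment, a negative answer off drug is a true answer, and six on-drug assessments (Weeks 1, 2, 4, 8, 12 and 16) precede any planned delgocitinib stop. Both statements stand. Even so, the late by-visit percentages are not rates among people using the cream.

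It can be said that sites would leave the question blank for someone off cream, so that the record drops out of the table. Nothing in the documents says so, and the SoA applies the EOT/ET item to the delgocitinib group without exception. Nor do they say that such participants record 0, so that remains an inference.

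Section 9 describes itself as a summary with technical detail left to the SAP, so a missing table rule is weak evidence by itself. Here, however, Section 9.3.1 does supply a rule, which is attendance.

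The strongest objection concerns the remedy. Participants still on drug late in the trial are largely those not cleared or those who relapsed. A table limited to them selects on response after randomisation. That stands and shapes the fix.

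**Conclusion.** The point holds for three descriptive summaries: the EOT/ET stinging/burning question, the investigator's local-tolerability summary at Weeks 20 and 24, and the vital-sign change to EOT/ET. As written, each mixes on-drug and off-drug records for responders who stopped and did not restart, with gaps of up to 8 weeks (delgocitinib) or 12 weeks (alitretinoin, vital signs only).

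The size cannot be determined from the documents. The fall from 10% to between 8% and 5% rests on three assumptions: an off-drug share of 20% to 50%, off-drug participants recording 0, and an on-drug rate that would be the same in everyone. The vital-sign figures also assume an effect size and full reversal.

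A reader might go further and infer a biased between-arm test on vital signs. No such test is planned: the summary is by group, and neither vital signs nor local tolerability is a listed endpoint. The primary analysis, all other efficacy analyses and the sample size are untouched. This is a change worth making to safety reporting, not a threat to the trial's conclusions.

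**What to change.** 1. In Sections 9.3.11.2 and 9.3.11.4, flag each EOT/ET record and each Week 20 and Week 24 tolerability record by days since last dose. Show participants dosed within 7 days and those off drug separately, beside the overall summary.
2. Build the flag from the daily treatment record in the eDiary (Section 6.4) and the last-administration date (Section 8.10.1). The diary is needed for Week 20, because a later restart moves the last-administration date. Show missing diary days as unknown, not as off drug.
3. Add an option to the EOT/ET question for no application in the last week.
4. Name the on-treatment weekly eDiary as the main source for the stinging/burning rate.
5. Reconcile Section 4.1, which presents stopping on IGA-CHE 0 or 1 as what participants will do, with Sections 6.2.1.1, 6.2.1.2 and 6.5.1, which present it as a recommendation. The point above holds under either reading.

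The cost is some analysis wording and one eCRF option, with no new visit or procedure. The groups shown become smaller. The late on-drug group is selected on response, so the split is descriptive and must not be read as a randomised comparison. It also cannot supply on-drug vital signs that were never scheduled, and the report should state that limit.

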8.2.7.2 Investigator's Assessment of Local Tolerability

The investigator will assess whether he/she suspects a local skin reaction related to application of the delgocitinib cream. If the investigator suspects a local skin reaction related to application of the delgocitinib cream, the skin reaction will be scored according to the Berger and Bowman scales in Table 8-9. The scoring should only assess skin signs suspected to be related to application of the delgocitinib cream and not signs or symptoms related to the participant's CHE.

Table 8-9 Berger and Bowman Scoring Scales if Investigator Suspects a Local Skin Reaction Related to Delgocitinib Application

Scale 1	
Skin appearance	Score
No evidence of irritation	0
Minimal erythema that is barely perceptible	1
Definite erythema that is readily visible and minimal oedema or minimal papular response	2
Erythema and papules	3
Definite oedema	4
Erythema, oedema, and papules	5
Vesicular eruption	6
Strong reaction spreading beyond the test field	7

Select the appropriate score (only 1 score) if a local skin reaction is suspected to be related to application of delgocitinib cream.

Scale 2	
Other observations	Letter score
Slightly glazed appearance	A
Markedly glazed appearance	В
Glazing with peeling and cracking	С
Glazing with fissures	F
Film of dried serous exudates covering all or part of the patch site	G
Small petechial erosions and/or scabs	Н

Other observations (multiple scores allowed) will be recorded if applicable.

For the investigator's assessment of local tolerability, it will be reported in the eCRF if the investigator suspects a local skin reaction to be related to application of delgocitinib (yes, no). If the investigator suspects a local skin reaction to be related to application of delgocitinib, the scores in Table 8-9 (1 score for Scale 1; and 0, 1, or multiple scores for Scale 2) will be recorded in the eCRF.

8.3 Adverse Events (AEs), Serious Adverse Events (SAEs), and Other Safety Reporting

The definitions of AEs and SAEs can be found in Appendix 3.

AEs reported by the participants or observed by the investigator must be recorded on the AE form of the eCRF (see Section 8.3.2).

The investigator and any qualified designees are responsible for detecting, documenting, and reporting events that meet the definition of an AE or SAE and remain responsible for following up all AEs (see Section 8.3.3). The method of recording, evaluating, and assessing causality of AEs and SAEs and the procedures for completing and transmitting SAE reports are provided in Appendix 3.

8.3.1 Time Period and Frequency for Collecting AE and SAE Information

All AEs and SAEs will be collected from the signing of the ICF until the end of trial (defined as attending the last visit in the trial [the ET visit, the nominal Week 24 visit, or the last follow-up visit, whichever comes last]), at the timepoints specified in the SoA (Table 1-1).

It will be recorded in the eCRF if the AE started prior to first administration of IMP.

All SAEs will be recorded and reported to the sponsor immediately without undue delay but no later than within 24 hours of awareness, as indicated in Appendix 3. The investigator will submit any updated SAE data to the sponsor within 24 hours of it being available.

Investigators are not obliged to actively seek information on new AEs or SAEs after the conclusion of trial participation. However, if the investigator learns of any SAE, including a death, at any time after a participant has been discharged from the trial, and he/she considers the event to be reasonably related to the IMP or trial participation, the investigator must promptly notify the sponsor.

8.3.2 Method of Detecting AEs and SAEs

Care will be taken not to introduce bias when detecting AEs and/or SAEs. Open-ended and non-leading verbal questioning of the participant is the preferred method to inquire about AE occurrence.

At all visits, participants will be asked a non-leading question by the investigator about AEs, e.g.: 'How have you felt since I saw you last?'. Participant-reported local tolerability will be

queried specifically (see Section 8.2.7.1) and reported as AE(s) if deemed relevant by the investigator.

When completing the TSQM PRO questionnaire, participants will be asked direct questions about side effects. If the participant answers 'yes' for item 3, and/or tick anything but 'not applicable' for items 4, 5 or 6 (see Section 8.1.3.5), the investigator must follow-up with the participant to ensure AEs are appropriately recorded.

If the AE qualifies as an SAE, expedited reporting is required (see Section 10.3.4). It is important that the investigator also observes the participant for any changes not reported by the participant and records these changes.

8.3.3 Follow-up of AEs and SAEs

After the initial AE/SAE report, the investigator is required to proactively follow-up with the participant at subsequent visits/contacts. All SAEs will be followed until resolution, stabilisation, until the event is otherwise explained, or the participant is lost to follow-up (as defined in Section 7.3). Further information on follow-up procedures is given in Appendix 3.

